Appendix II

Patient Thank You Letter

We ask that the physician use the template contained in this appendix to prepare a letter thanking the patient for enrolling in this trial. The template is intended as a guide and can be downloaded from the web site at <http://www.ecog.org>. As this is a personal letter, physicians may elect to further tailor the text to their situation.

This small gesture is a part of a broader program being undertaken by ECOG-ACRIN and the NCI to increase awareness of the importance of clinical trials and improve accrual and follow-through. We appreciate your help in this effort.

[PATIENT NAME]

[DATE]

[PATIENT ADDRESS]

Dear [PATIENT SALUTION],

Thank you for agreeing to take part in this important research study. Many questions remain unanswered in cancer. With the participation of people like you in clinical trials, we hope to improve treatment and quality of life for those with your type of cancer.

We believe you will receive high quality, complete care. I and my research staff will maintain very close contact with you. This will allow me to provide you with the best care while learning as much as possible to help you and other patients.

On behalf of **[INSTITUTION]** and ECOG-ACRIN, we thank you again and look forward to helping you.

Sincerely,

[PHYSICIAN NAME]

A Phase II Neoadjuvant Study of Encorafenib With Binimetinib in Patients With Resectable Locoregional Metastases From Cutaneous or Unknown Primary Melanoma (Stages III N1B/C/D)

Appendix III

Patient Pill Calendar

NOTE TO SITES: Local study teams may use a different calendar format as long as all drug/ dates/ doses are recorded for study reporting/ data completion. These should be shared with the Site Principal Investigator and approved by local IRBs per local guidelines, prior to use.

Pill Calendar Directions

1. Take your scheduled dose of each pill.
2. If you forget, the missed pills will not be taken later.
3. Please bring the empty bottle or any leftover tablets and your pill calendar to your next clinic visit.

Patient Pill Calendar

This is a calendar on which you are to record the time and number of tablets you take each day for Encorafenib and Binimatinib. You should take your scheduled dose of each pill. **Note the times and the number of tablets that you take each day.** If you develop any side effects, please record them and anything you would like to tell the doctor in the space provided. Bring any unused tablets and your completed pill calendar to your doctor's visits.

Instructions:

Encorafenib: Take by mouth once daily
Pills should be swallowed whole and may be taken with or without food.
Dose of each pill: 75 mg
Number of pills to take at each dose: _____ capsules
Total dose to take each day: _____ mg

Binimatinib: Take by mouth twice daily
Pills should be swallowed whole and may be taken with or without food.
Dose of each pill: 15 mg
Number of pills to take at each dose: _____ tablets
Total dose to take at each dose: _____ mg

- Doses of Binimatinib that are missed should not be taken within 6 hours prior to the next scheduled dose.
- Doses of Encorafenib that are missed should not be taken within 12 hours prior to the next scheduled dose.
- If vomiting occurs after taking either medication, the dose should not be repeated

CYCLE DAY	Date		Encorafenib		Binimatinib			Use the space below to make notes about things you would like to tell the doctor (including unusual symptoms you experience, other medicine you have taken and anything else you think would be of interest.)
	(Month/ Day/ Year)		# Capsules	Time taken	# Tablets	Time Taken AM	Time Taken PM	
1								
2								
3								
4								
5								
6								
7								
8								

CYCLE DAY	Date		Encorafenib		Binimatinib		Use the space below to make notes about things you would like to tell the doctor (including unusual symptoms you experience, other medicine you have taken and anything else you think would be of interest.)
	(Month/ Day/ Year)		# Capsules	Time taken	# Tablets	Time Taken AM	
9							
10							
11							
12							
13							
14							
15							
16							
17							
18							
19							
20							
21							
22							
23							
24							
25							
26							
27							
28							
Signature of staff (End of cycle)							
Date							

A Phase II Neoadjuvant Study of Encorafenib With Binimetinib in Patients With Resectable Locoregional Metastases From Cutaneous or Unknown Primary Melanoma (Stages III N1B/C/D)

Appendix IV

ECOG Performance Status

PS 0	Fully active, able to carry on all pre-disease performance without restriction
PS 1	Restricted in physically strenuous activity but ambulatory and able to carry out work of a light or sedentary nature e.g., light house work, office work.
PS 2	Ambulatory and capable of all self-care but unable to carry out any work activities. Up and about more than 50% of waking hours.
PS 3	Capable of only limited self-care, confined to bed or chair more than 50% of waking hours.
PS 4	Completely disabled. Cannot carry on any self-care. Totally confined to bed or chair.

A Phase II Neoadjuvant Study of Encorafenib With Binimetinib in Patients With Resectable Locoregional Metastases From Cutaneous or Unknown Primary Melanoma (Stages III N1B/C/D)

Appendix V

Instructions for Reporting Pregnancies on a Clinical Trial

What needs to be reported?

All pregnancies and suspected pregnancies (including a positive or inconclusive pregnancy test regardless of age or disease state) of a female patient while she is on encorafenib and binimetinib or ¹⁸F-FLT within 28 days of the female patient's last dose of encorafenib, binimetinib or ¹⁸F-FLT must be reported in an expeditious manner. The outcome of the pregnancy and neonatal status must also be reported.

How should the pregnancy be reported?

The pregnancy, suspected pregnancy (including a positive or inconclusive pregnancy test) must be reported via CTEP's Adverse Event Reporting System (CTEP-AERs).

http://ctep.cancer.gov/protocolDevelopment/electronic_applications/adverse_events.htm

When does a pregnancy, suspected pregnancy or positive/inconclusive pregnancy test need to be reported?

An initial report must be done within 24 hours of the Investigator's learning of the event, followed by a complete expedited CTEP-AERs report within 5 calendar days of the initial 24-hour report.

What other information do I need in order to complete the CTEP-AERs report for a pregnancy?

- The pregnancy (fetal exposure) must be reported as a Grade 3 "Pregnancy, puerperium and perinatal conditions – Other (pregnancy)" under the System Organ Class (SOC) "Pregnancy, puerperium and perinatal conditions"
- The pregnancy must be reported within the timeframe specified in the Adverse Event Reporting section of the protocol for a grade 3 event.
- The start date of the pregnancy should be reported as the calculated date of conception.
- The potential risk of exposure of the fetus to the investigational agent(s) or chemotherapy agent(s) should be documented in the "Description of Event" section of the CTEP-AERs report.

What else do I need to know when a pregnancy occurs to a patient?

- The Investigator must follow the female patient until completion of the pregnancy and must report the outcome of the pregnancy and neonatal status via CTEP-AERS.
- The decision on whether an individual female patient can continue protocol treatment will be made by the site physician in collaboration with the study chair and ECOG-ACRIN Operations Office – Boston. Please contact the ECOG-ACRIN Operations Office – Boston to ask for a conference call to be set up with the appropriate individuals.
- *It is recommended the female patient be referred to an obstetrician-gynecologist, preferably one experienced in reproductive toxicity for further evaluation and counseling.*

How should the outcome of a pregnancy be reported?

The outcome of a pregnancy should be reported as an *amendment* to the initial CTEP-AERs report if the outcome occurs on the same cycle of treatment as the pregnancy itself. However, if the outcome of the pregnancy occurred on a subsequent cycle, a *new* and separate CTEP-AERs report should be initiated reporting the outcome of the pregnancy.

What constitutes an abnormal outcome?

An abnormal outcome is defined as any pregnancy that results in the birth of a child with persistent or significant incapacity or substantial disruption of the ability to conduct normal life functions (formerly referred to as disabilities), congenital anomalies, or birth defects. For assistance in recording the grade or category of these events, please contact the CTEP AEMD Help Desk at [contact] or [contact], for it will need to be discussed on a case by case basis.

Reporting a Pregnancy Loss

A pregnancy loss is defined in CTCAE as “*A death in utero*.”

It must be reported via CTEP-AERS as a Grade 4 “*Pregnancy Loss*” under the System Organ Class (SOC) “*Pregnancy, puerperium and perinatal conditions*”.

A pregnancy loss should **NOT** be reported as a Grade 5 event as currently CTEP-AERS recognizes this event as a patient’s death

Reporting a Neonatal Death

A neonatal death is defined in CTCAE as “*A death occurring during the first 28 days after birth*” that is felt by the investigator to be at least possibly due to the investigational agent/intervention. However, for this protocol, any neonatal death that occurs within 28 days of birth, without regard to causality AND any infant death after 28 days that is suspected of being related to the *in utero* exposure to encorafenib, binimatinib or ¹⁸F-FLT must also be reported via CTEP-AERS. It must be reported via CTEP-AERS as a Grade 4 “*Death neonatal*” under the System Organ Class (SOC) “General disorder and administration site conditions”.

Additional Required Forms:

When submitting CTEP-AERs reports for pregnancy, pregnancy loss, or neonatal loss, the **CTEP ‘Pregnancy Information Form’** must be completed and faxed along with any additional medical information to CTEP [contact]). This form is available on CTEP's website

(http://ctep.cancer.gov/protocolDevelopment/electronic_applications/docs/PregnancyReportForm.pdf)

A Phase II Neoadjuvant Study of Encorafenib With Binimetinib in Patients With Resectable Locoregional Metastases From Cutaneous or Unknown Primary Melanoma (Stages III N1B/C/D)

Appendix VI

Contraception Guidance

Patients of Childbearing Potential

A patient is considered fertile following menarche and until becoming post-menopausal unless permanently sterile (see below). If fertility is unclear (e.g., amenorrhea in adolescents or athletes) and a menstrual cycle cannot be confirmed before first dose of study treatment, additional evaluation should be considered.

Patients in the following categories are **not** considered of child-bearing potential

1. Premenarchal
2. Premenopausal patient with 1 of the following:
 - Documented hysterectomy
 - Documented bilateral salpingectomy
 - Documented bilateral oophorectomy

For individuals with permanent infertility due to an alternate medical cause other than the above, (e.g., mullerian agenesis, androgen insensitivity), Investigator discretion should be applied to determining study entry.

NOTE: Documentation can come from the site personnel's: review of the patient's medical records, medical examination, or medical history interview.

3. Postmenopausal patient
 - A postmenopausal state is defined as no menses for 24 months without an alternative medical cause.
 - A high follicle stimulating hormone (FSH) level in the postmenopausal range may be used to confirm a postmenopausal state in patients not using hormonal contraception or hormonal replacement therapy (HRT). However, in the absence of 24 months of amenorrhea, confirmation with more than one FSH measurement is required.
 - Patients on HRT and whose menopausal status is in doubt will be required to use one of the non-estrogen hormonal highly effective contraception methods if they wish to continue their HRT during the study. Otherwise, they must discontinue HRT to allow confirmation of postmenopausal status before study enrollment.

NOTE: **There is a potential for encorafenib to induce CYP3A4, which may reduce the effectiveness of hormonal contraception methods. Therefore, the use of at least 1 form of non-hormonal contraception is required for patients of childbearing potential during participation in this study.**

The contraception guidelines outlined below are adapted from the recommendations related to contraception and pregnancy testing in clinical trials guidance document (Clinical Trials Facilitation Group Guidelines 2014). Patients must agree to use highly effective methods of

contraception if it is mandated locally or when, in the judgment of the Investigator, compliance with acceptable methods is likely to be suboptimal.

The following methods have been classified as being highly effective (i.e., failure rate < 1% per year when used consistently and correctly) in preventing a pregnancy:

- Complete abstinence from heterosexual intercourse during the entire period of risk associated with the study treatments; the reliability of sexual abstinence should be evaluated in relation to the duration of the clinical trial and the preferred and usual lifestyle of the participant
- Combined (estrogen and progestogen containing) hormonal contraception associated with inhibition of ovulation:
 - Oral
 - Intravaginal
 - Transdermal
- Progestogen-only hormonal contraception associated with inhibition of ovulation:
 - Oral
 - Injectable
 - Implantable
- Intrauterine device (IUD)
- Intrauterine hormone-releasing system (IUS)
- Bilateral tubal occlusion
- Vasectomised partner (considered highly effective provided the vasectomized partner has received medical assessment of surgical success and that the partner is a female participant's sole sexual partner)

Acceptable birth control methods characterized as having a failure rate of more than 1% per year include:

- Progestogen-only oral hormonal contraception, where inhibition of ovulation is not the primary mode of action
- Male or female condom with or without spermicide
- Cap, diaphragm or sponge with spermicide

A Phase II Neoadjuvant Study of Encorafenib With Binimetinib in Patients With Resectable Locoregional Metastases From Cutaneous or Unknown Primary Melanoma (Stages III N1B/C/D)

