A patient of childbearing potential is defined as anyone, regardless of sexual orientation or whether they have undergone tubal ligation, who meets the following criteria: 1) has achieved menarche at some point, 2) has not undergone a hysterectomy or bilateral oophorectomy; or 3) has not been naturally postmenopausal (amenorrhea following cancer therapy does not rule out childbearing potential) for at least 24 consecutive months (i.e., has had menses at any time in the preceding 24 consecutive months).

Patient of childbearing potential? _____ (Yes or No)

Date of blood test or urine study: _____

_____ 3.1.21 Patients must not expect to conceive or father children by using accepted and effective method(s) of contraception (please refer to [Appendix VI](#)) or to abstain from sexual intercourse from the time of registration, while on study treatment and for at least 30 days after the last dose of protocol treatment for female patients, and for at least 90 days after the last dose of protocol treatment for male patients. In addition, patients must not donate ova from the time of registration until 30 days after the last dose of study treatment or donate sperm from the time of registration until 90 days after the last dose of protocol treatment.

_____ 3.1.22 Patient must not have known hypersensitivity or contraindication to any component of binimetinib or encorafenib or their excipients.

_____ 3.1.23 Patient must not have impaired cardiovascular function or clinically significant cardiovascular disease including, but not limited to, any of the following:

_____ 3.1.23.1 History of acute coronary syndromes (including myocardial infarction, unstable angina, coronary artery bypass grafting, coronary angioplasty or stenting) < 6 months prior to registration:

_____ 3.1.23.2 Congestive heart failure requiring treatment (New York Heart Association Grade ≥ 2).

- _____ 3.1.23.3 Left ventricular ejection fraction (LVEF) < 50% as determined by MUGA or ECHO.
- _____ 3.1.23.4 Uncontrolled hypertension defined as persistent systolic blood pressure \geq 150 mmHg or diastolic blood pressure \geq 100 mmHg despite current therapy.
- _____ 3.1.23.5 History or presence of clinically significant cardiac arrhythmias (including resting bradycardia, uncontrolled atrial fibrillation or uncontrolled paroxysmal supraventricular tachycardia).
- _____ 3.1.23.6 Baseline QTc interval \geq 480 ms.

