- _____ 3.1.24 Patient must not have impairment of gastrointestinal function or disease which may significantly alter the absorption of study drug (e.g., active ulcerative disease, uncontrolled vomiting or diarrhea, malabsorption syndrome, small bowel resection with decreased intestinal absorption), or recent (\leq 3 months) history of a partial or complete bowel obstruction, or other conditions that will interfere significantly with the absorption of oral drugs.
- _____ 3.1.25 Patient must not have any known history of acute or chronic pancreatitis.
- _____ 3.1.26 Patient must not have any concurrent neuromuscular disorder that is associated with elevated CK (e.g., inflammatory myopathies, muscular dystrophy, amyotrophic lateral sclerosis, spinal muscular atrophy).
- _____ 3.1.27 Patient must not have any known history or current evidence of Retinal Vein Occlusion (RVO) or current risk factors for RVO (e.g., uncontrolled glaucoma or ocular hypertension, history of hyperviscosity, factor V Leiden or activated protein C resistance); history of retinal degenerative disease.
- _____ 3.1.28 Patient must not use any medication (including herbal medications, supplements, or foods), as described in Section [8.1.14](#) and Section [8.2.15](#), or use of a prohibited medication \leq 1 week prior to registration. See [Appendix X](#).
- _____ 3.1.29 Patient may be on anticoagulation at prophylactic or therapeutic levels. Patients must not be using specific anticoagulants at therapeutic levels that may interfere with encorafenib and binimetinib. See [Appendix X](#).
- _____ 3.1.30 Patient must not have a history of thromboembolic or cerebrovascular events \leq 12 weeks prior to registration. Examples include transient ischemic attacks, cerebrovascular accidents, hemodynamically significant (i.e. massive or sub-massive) deep vein thrombosis or pulmonary emboli.

NOTE: Patients with thromboembolic events related to indwelling catheters or other procedures may be registered.

NOTE: Patients with either deep vein thrombosis or pulmonary emboli that does not result in hemodynamic instability are

allowed to register as long as they are on a stable dose of anticoagulants for at least 4 weeks.

Physician Signature

Date

OPTIONAL: This signature line is provided for use by institutions wishing to use the eligibility checklist as source documentation.

4. Registration Procedures

CTEP Registration Procedures

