8.2.15 Concomitant Medications

Encorafenib is a reversible inhibitor of CYP1A2, CYP2B6, CYP2C8, CYP2C9, CYP3A4 and UGT1A1. It is also a time-dependent inhibitor of CYP3A4, and induced CYP2B6, CYP2C9 and CYP3A4 in human primary hepatocytes. Permitted medications to be used with caution in this study include those that are sensitive substrates of CYP1A2, CYP2B6, CYP2C9, CYP2C9, CYP3A4, and UGT1A1 or those substrates that have a narrow therapeutic index.

There is a potential for encorafenib to induce CYP3A4, which may reduce the effectiveness of hormonal contraception methods. Therefore, the use of at least 1 form of non-hormonal contraception is required for females of childbearing potential during participation in this study. Caution should be used in patients receiving concomitant treatment with other drugs that are substrates of CYP3A4 as the efficacy of these drugs could be reduced when administered with encorafenib.

Encorafenib has been identified in vitro to be metabolized by CYP3A4 and to a lesser extent by CYP2C19. The use of strong inhibitors of CYP3A4 is prohibited. Concomitant use of moderate CYP3A4

inhibitors while on study should be avoided. If use of moderate CYP3A4 inhibitors is unavoidable and no alternatives are available, short-term use (≤ 30 days) is permitted with accompanying dose reduction to one-half of the encorafenib dose prior to use of moderate CYP3A4 inhibitors (or as close as can be achieved without exceeding the target dose). The encorafenib dose that was taken prior to initiating the CYP3A4 inhibitor may be resumed after the inhibitor has been discontinued for 3 to 5 elimination half-lives. Strong inhibitors of CYP2C19 should be used with caution when co-administered with encorafenib. Use of moderate and strong inducers of CYP3A4 is prohibited.

In vitro data showed that encorafenib is a substrate of the transporter P-gp. Thus, drugs that are known to inhibit or induce P-gp should be used with caution. Encorafenib is also a potent inhibitor of the renal transporters, OAT1, OAT3 and OCT2, and the hepatic transporters OATP1B1 and OATP1B3. The co-administration of drugs that are known to be sensitive or narrow therapeutic index substrates of OAT1, OAT3, OCT2, OATP1B1 or OATP1B3 should be used with caution.

Prohibited Concomitant Therapy

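### Appendix VI makes a hormonal contraceptive the condition for staying on HRT when menopausal status is in doubt, although the protocol warns that encorafenib may weaken hormonal methods

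*Combined protocol and SAP*

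**What the plan says.** Appendix VI, item 3 (postmenopausal patients), covers patients taking HRT whose menopausal status is uncertain. Such a patient "will be required to use one of the non-estrogen hormonal highly effective contraception methods if they wish to continue their HRT during the study". The only stated alternative is to stop HRT so that her status can be confirmed before she enrolls.

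The NOTE immediately below gives a possible CYP3A4 interaction with encorafenib as its reason and adds that "the use of at least 1 form of non-hormonal contraception is required for patients of childbearing potential during participation in this study". Section 8.2.15 carries the same warning, that the interaction "may reduce the effectiveness of hormonal contraception methods", and the same non-hormonal requirement.

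Appendix VI then sorts methods into two classes. Highly effective methods fail in under 1% of users per year. Acceptable methods, such as condoms, fail in more than 1% per year. Criterion 3.1.21 asks for "accepted and effective method(s) of contraception" and sends the reader to Appendix VI for the detail.

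**The concern.** The HRT rule and the interaction warning point in opposite directions. A patient whose fertility has not been ruled out is told to use a hormonal method, and the next paragraph says that the study drug may weaken hormonal methods. The position of the rule adds some doubt, because it is printed in the list of patients who are not "considered of child-bearing potential", whereas the NOTE addresses patients who are.

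What is at stake is pregnancy on treatment. Section 8.1.15 says that binimetinib must not be used in pregnant women. The rule also has a practical effect: it does not recognise the listed methods that are both highly effective and untouched by the interaction.

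**Working it through.** The plan gives no figure to reproduce here. The check sets the highly effective methods listed in Appendix VI against the two requirements, first on the plain reading of the HRT rule, which is a hormonal method without estrogen.

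| Highly effective method | Meets HRT rule | Meets NOTE (non-hormonal) |
|---|---|---|
| Abstinence | no | yes |
| Combined hormonal | no | no |
| Progestogen-only, ovulation-inhibiting | yes | no |
| Intrauterine device | no | yes |
| Hormone-releasing intrauterine system | yes | no |
| Tubal occlusion | no | yes |
| Vasectomised partner | no | yes |

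**Step 1, counts.** Seven methods are listed. Two meet the HRT rule: "Progestogen-only hormonal contraception associated with inhibition of ovulation" and the hormone-releasing intrauterine system. Four meet the NOTE. The overlap is 0.

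**Step 2, meaning of the overlap.** The two requirements add together, because the NOTE does not forbid a hormonal method. An overlap of 0 means that no single method is enough. It does not mean that she cannot comply.

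**Step 3, does the NOTE reach her?** Appendix VI opens by treating a patient past menarche as fertile until she is postmenopausal, unless she is permanently sterile. A patient whose status is in doubt has not been shown to be postmenopausal. The definition of childbearing potential in 3.1.20 points the same way. The better reading is that the NOTE applies to her despite the heading of the list.

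**Step 4, which combinations comply?**
- Progestogen-only method plus condom: complies. The first meets the HRT rule and the second meets the NOTE, which does not ask for a highly effective method.
- Intrauterine device, tubal occlusion or vasectomised partner alone: meets the NOTE but not the HRT rule as worded.

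**Step 5, how good is the complying pair?** The documents do not say how far encorafenib weakens hormonal methods, so only a range can be given. With no weakening, the progestogen method alone stays under 1% failure per year. If its effect were lost entirely, she would rely on the condom, which is classed above 1%. The pair therefore stays in the highly effective class only if the interaction is small or absent. The non-hormonal methods that the rule leaves out are in that class whatever the interaction.

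**Step 6, looser reading.** If the phrase means any method without estrogen, 7 - 1 = 6 methods meet the HRT rule, and the four non-hormonal ones meet both requirements alone. Two of the six are still hormonal, so progestogen plus condom still complies.

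**Step 7, duration.** Dosing is planned for 52 weeks, and contraception continues for 30 days after the last dose: 52 x 7 + 30 = 394 days. This leaves out the time from registration to first dose and the break for surgery. It describes how long the rule matters and does not measure risk.

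**The case against.** The strongest reply is that the patient is already protected. On the better reading she needs a non-hormonal method in addition to the hormonal one, which is more than the appendix asks of a clearly fertile patient. For such a patient, a highly effective method is demanded only where local rules require it or the investigator doubts compliance. She may also stop HRT instead, and pregnancy is tested before registration and again before adjuvant treatment. On the looser reading of the phrase, an intrauterine device alone would do.

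Most of this stands, and it keeps the point minor. It does not remove the mismatch. The HRT bullet is where the appendix insists on a highly effective method for this group, and on its plain wording only hormonal methods meet that standard. The looser reading is possible but is not what the words say.

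Two stronger inferences are tempting and are not supported:
- **A hormonal method alone complies.** A reader might infer this from the heading above the HRT rule. It gives the position of a bullet more weight than the appendix's opening statement on fertility and the definition in 3.1.20.
- **Appendix VI permits HRT that contains a prohibited drug.** A reader might infer this because Appendix X lists progesterone as a CYP3A4 inducer and Appendix VI does not limit the content of HRT. But Section 8.2.15 already states: "Use of moderate and strong inducers of CYP3A4 is prohibited". Criterion 3.1.28 also excludes the "or use of a prohibited medication" in the week before registration and refers to Appendix X. Silence in a contraception appendix does not override those rules. Appendix X also names progesterone only, not progestogens as a class, so it does not show that progestogen contraceptives are banned.

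**Conclusion.** The inconsistency is real and minor. As worded, Appendix VI steers HRT users of uncertain menopausal status to a class of contraceptive that the protocol says may be weakened, and it gives no credit to highly effective non-hormonal methods used alone. The likely result is two methods, of which the non-hormonal one need not be highly effective. It is not a patient left on a hormonal method only.

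This rests on two readings: that the HRT rule means a hormonal method without estrogen, and that the NOTE covers these patients. Section 9.6 expects 15 women among 42 patients, but the documents do not say how many would be on HRT with uncertain status. No patient count is claimed, and the number is likely small. No effect on pCR or any other endpoint follows.

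**What to change.** In the HRT bullet of Appendix VI, change *non-estrogen hormonal highly effective* to *non-hormonal highly effective*. Abstinence, an intrauterine device, tubal occlusion or a vasectomised partner would then each satisfy both the HRT rule and the NOTE, and a progestogen method plus a condom would no longer be enough. A clause stating that the NOTE covers patients on HRT with uncertain menopausal status would be helpful but is optional.

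The cost is one phrase in an amendment, with no added tests and no design change. A few HRT users may have to choose a different method.
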